7.1.3. SAS codes to run ANCOVA (using PROC MIXED) on MI data

```

*** MULTIPLE IMPUTATIONS ***;
*** PROC MIXED ***;
ods output LSMESTIMATEs=outlsmean0(rename=(label=PARAMETER));
proc mixed data=din;
  by AVISIT PARAMN INPUT;
  CLASS TRTPN (ref=last);
  MODEL CHG=TRTPN BASE;
  LSMESTIMATE TRTPN "OTX-DED 0.2MG" 1 0 0,
    "OTX-DED 0.3MG" 0 1 0,
  /* WG1 and WG2 are the sample size weighted coefficient for group 1 and 2 respectively*/
    "Overall OTX-DED" &WG1. &WG2. 0,
    "HV" 0 0 1,
    "OTX-DED 0.2MG vs HV" 1 0 -1 ,
    "OTX-DED 0.3MG vs HV" 0 1 -1 ,
    "Overall OTX-DED vs HV" &WG1. &WG2. -1 / cl;
  run;

ods output ParameterEstimates=outlsmean1;
PROC MIANALYZE DATA=outlsmean0;
  modeleffects estimate;
  stderr stderr;
  by avisit PARAMN PARAMETER;
RUN;

```

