2.3. Randomization and Masking

Subjects will be randomized to treatment assignment.

A randomization schedule will be computer-generated by a qualified biostatistician independent of the study conduct or project team and uploaded into the EDC system. The EDC/IRT system will be used for randomization and unmasking. The OTX-DED and HV inserts administered to subjects at randomization in the double-masked treatment phase will be comparable in appearance. Eligible subjects will be randomly assigned to one of three treatment groups (OTX-DED 0.2mg, OTX-DED 0.3mg, or HV) in a 1:1:1 ratio.

Study subjects and investigators and their staff will be masked to the identity of treatment until the final database is locked. The Sponsor's personnel involved with the conduct and monitoring of the study will remain masked until completion of the study and database lock.

Sponsor:	Ocular Therapeutix, Inc.		
Protocol:	OTX-DED-2020-201		
Document Version No.:	V1.0	Document Date:	11NOV2021

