4. STATISTICAL METHODS

4.1. Sample Size Justification

This study is not powered to show statistical significance but will provide initial estimates and trends of the endpoints for use in future trial designs. The sample size will allow for safety information to be obtained, while still limiting the number of subjects exposed to the IP. Statistical analyses will be descriptive.

The trial will include approximately 150 subjects (300 eyes) from approximately 15 sites.

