4.2. General Statistical Methods and Data Handling

4.2.1. General Methods

All output will be incorporated into Microsoft Excel or Word files, sorted, and labeled according to the International Council on Harmonisation (ICH) recommendations, and formatted to the appropriate page size(s).

Tabulations will be produced for appropriate demographic, baseline, efficacy, and safety parameters. For categorical variables, summary tabulations of the number and percentage of each category of the parameter will be presented by treatment groups and visits (as applicable). For continuous variables, the n, mean, standard deviation, median, minimum, and maximum values will be presented.

The baseline visit will be defined as the last non-missing measure prior to initiation of IP. Differences between treatment groups will be calculated as OTX-DED minus HV and change from baseline will be calculated as follow up visit minus baseline visit values. In addition to looking at the individual formulations, the two formulations of OTX-DED will be combined and summarized.

All statistical testing will be done at the two-sided alpha level of 0.05, with no adjustments due to multiple endpoints testing.

Sponsor:	Ocular Therapeutix, Inc.		
Protocol:	OTX-DED-2020-201		
Document Version No.:	V1.0	Document Date:	11NOV2021

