4.2.9.1. Imputation Method for Primary Efficacy Endpoints

To impute missing, Markov Chain Monte Carlo (MCMC) multiple imputation (MI), Fully Conditional Specification multiple imputation (FCS MI) and LOCF methods will be used.

For MI, we will have below phases:

1. Imputation Phase: in this phase, the missing data will be imputed using SAS PROC MI and a complete data set will be created. This process of imputation will be repeated 25 times. Therefore, 25 compete datasets will be created. In this phase, treatment group, baseline value, and post-baseline visits will be included in multiple imputation model.
2. Analysis Phase: each of the 25 complete data sets will be analyzed independently using desired statistical method (e.g. ANCOVA for primary efficacy analysis).
3. Pooling Phase: in this phase the estimates obtained from each analyzed complete dataset from phase 2, will be combined using PROC MIANALYZE.

The primary analyses of efficacy data will use MCMC MI methodology to impute missing data. The expectation and maximization (EM) algorithm will be used to estimate the mean vector and the covariance assuming a missing at random (MAR) distribution. The MAR distribution assumes the probability that a value is missing does not depend on the true values of the missing items. The imputation phase will create 25 copies of the dataset which will contain different estimates of the missing values. The 25 complete datasets will then be analyzed to produce several sets of parameter estimates and standard errors, which will then be pooled to create a single set of results.

Last observation carried forward (LOCF) method and Fully Conditional Specification multiple imputation (FCS MI) with 200 burn-in iterations and 25 times of imputation under the assumption of missingness at random will be used for sensitivity analyses (Section 4.7.2).

Sponsor:	Ocular Therapeutix, Inc.		
Protocol:	OTX-DED-2020-201		
Document Version No.:	V1.0	Document Date:	11NOV2021

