7.1.4. SAS codes to run t-test on MI data

```

/* SAS code below for testing group 1 vs group 3*/
ods output statistics=ttest1;
proc ttest data=din;
  where TRTPN in (1 3) ;
  by AVISIT PARAMN INPUT;
  class TRTPN;
  var CHG;
run;

ods output parameterestimates=pdif;
proc mianalyze data=ttest2;
  modeleffects mean;
  stderr stderr;
  by AVISIT PARAMN Class;
run;

```

7.1.5. SAS codes to run ANCOVA (using PROC MIXED) on Observed data and LOCF

Sponsor:	Ocular Therapeutix, Inc.		
Protocol:	OTX-DED-2020-201		
Document Version No.:	V1.0	Document Date:	11NOV2021

```
*** PROC MIXED ***;
ods output LSMESTIMATES=ls1(rename=(label=PARAMETER)) DIFFS=dun1;
proc mixed data=din;
by PARAMN AVISITN;
CLASS TRTPN (ref=last);
MODEL CHG=TRTPN BASE;
lsmeans TRTPN / cl pdiff=control('3') adjust=Dunnett;
LSMESTIMATE TRTPN "OTX-DED 0.2MG" 1 0 0,
"OTX-DED 0.3MG" 0 1 0,
"Overall OTX-DED" &WG1. &WG2. 0,
"HV" 0 0 1,
"OTX-DED 0.2MG vs HV" 1 0 -1,
"OTX-DED 0.3MG vs HV" 0 1 -1,
"Overall OTX-DED vs HV" &WG1. &WG2. -1 / cl;
run;
```

7.1.6. **SAS codes to output 95% CI for proportions using Clopper-Pearson method and 95% CI for the proportion difference using Chan and Zhang (1999) method using observed and LOCF data**

```
ods output RiskDiffCol1=freq1(where=(ROW in ("Row 1" "Row 2" "Difference")));
FishersExact=freq2(where=(NAME1="XP2_FISH"));
proc freq data=din;
where TRTPN in (1 3) and avisitn=4;
table TRTPN*AVALN / norow nocol nopercent fisher;
exact riskdiff(method=score);
run;
```

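### The MI pooling code gives PROC MIANALYZE no complete-data degrees of freedom, so intervals in the MI sensitivity analyses are about 1% too narrow

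*SAP*

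**What the plan says.** SAP 4.2.9.1 describes imputing 25 times, analysing each completed data set and pooling with PROC MIANALYZE. On what is pooled it says: "The 25 complete datasets will then be analyzed to produce several sets of parameter estimates and standard errors". It does not mention degrees of freedom.

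The code follows that description. In SAP 7.1.3 the model is "MODEL CHG=TRTPN BASE". The LSMESTIMATE rows go to "PROC MIANALYZE DATA=outlsmean0", which reads only the estimate and its standard error, by visit, parameter and contrast. In SAP 7.1.4 the example t-test is restricted by "where TRTPN in (1 3"), and pooling uses "proc mianalyze data=ttest2", again with only a mean and a standard error, by visit, parameter and Class. EDF= appears in neither call.

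On the role of these analyses, SAP 4.7.1 and 5 make observed data with Dunnett's adjustment the primary analysis. SAP 4.7.2 makes MCMC MI and FCS MI sensitivity analyses without a multiplicity adjustment. SAP 4.7.3 applies the same sensitivity set to the VAS scores, investigator-rated hyperemia, and total and regional corneal staining. The test level is set in SAP 4.2.1: "All statistical testing will be done at the two-sided alpha level of 0.05, with no adjustments due to multiple endpoints testing".

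**The concern.** Without EDF=, PROC MIANALYZE treats the complete-data degrees of freedom as infinite. The pooled degrees of freedom then depend only on the number of imputations and the share of between-imputation variance. With 25 imputations and modest missingness they run into the thousands, well above what a trial of this size can support.

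A missing-data sensitivity analysis should differ from its observed-data counterpart only in how missing values are handled. Here the reference distribution changes too, and the SAP does not say so. The effect can be isolated where Dunnett's adjustment plays no part on either side:

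- the Overall OTX-DED against HV contrast, which is an unadjusted LSMESTIMATE both in the observed-data code (SAP 7.1.5) and in the MI code (SAP 7.1.3);
- the two-sample t-tests, which are unadjusted throughout.

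For these, a small part of any change in p-value after imputation comes from the code and not from the missing data. The same blocks serve several endpoints, two populations and both eyes, so the omission repeats across many tables.

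**Working it through.** The documents state no degrees of freedom or critical values for the pooled analyses, so there is no planned figure to reproduce.

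**Inputs**
- Two-sided alpha 0.05 (SAP 4.2.1).
- Size: "The trial will include approximately 150 subjects (300 eyes) from approximately 15 sites" (SAP 4.1), with 50 per arm in SAP Table 1 and 1:1:1 allocation (SAP 2.3). One study eye per subject is analysed.
- Imputations m = 25 (SAP 4.2.9.1).
- Complete-data df, v0:
  - ANCOVA: three arm means plus one baseline slope, 150 − 4 = 146.
  - t-test, one dose against HV: 50 + 50 − 2 = 98.
  - t-test, combined doses against HV: 100 + 50 − 2 = 148.
- Fraction of missing information g: not given. Assumed 0.03 to 0.15.

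**Formulas**
- Default (Rubin) df: v_m = (m − 1)/g².
- Small-sample (Barnard–Rubin) df: 1/(1/v_m + 1/v_obs), with v_obs = (1 − g)·v0·(v0 + 1)/(v0 + 3).
- Narrowing: 1 − t(0.975; default df)/t(0.975; small-sample df).

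**Worked case, ANCOVA, g = 0.10**
- v_m = 24/0.01 = 2400, critical value 1.961.
- v_obs = 0.90 × 146 × 147/149 = 129.6.
- Small-sample df = 1/(1/2400 + 1/129.6) = 123.0, critical value 1.979.
- Narrowing = 1 − 1.9610/1.9794 = 0.93%. The tail area beyond the coded value at 123 df is 0.0521.

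**Range**

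| Analysis | g | Default df | Small-sample df | Coded critical value | Small-sample critical value | Too narrow by | Nominal 0.05 becomes |
|---|---|---|---|---|---|---|---|
| ANCOVA (146) | 0.03 | 26667 | 139 | 1.960 | 1.977 | 0.87% | 0.0520 |
| ANCOVA (146) | 0.15 | 1067 | 110 | 1.962 | 1.982 | 0.99% | 0.0523 |
| t-test, one dose (98) | 0.03 | 26667 | 93 | 1.960 | 1.986 | 1.30% | 0.0530 |
| t-test, one dose (98) | 0.15 | 1067 | 76 | 1.962 | 1.992 | 1.48% | 0.0534 |
| t-test, combined (148) | 0.03 | 26667 | 141 | 1.960 | 1.977 | 0.85% | 0.0520 |
| t-test, combined (148) | 0.15 | 1067 | 111 | 1.962 | 1.982 | 0.98% | 0.0522 |

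A p-value of 0.050 on the small-sample df prints as about 0.048 from the ANCOVA code and about 0.047 from the single-dose t-test code.

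**Share of the gap to the primary.** For one dose against HV, the primary ANCOVA uses Dunnett's two-sided value for two comparisons with a control: 2.234 at 146 df with equal arms. At g = 0.10 the coded MI value is 1.961, and with EDF= it would be 1.979. The whole gap is 2.234 − 1.961 = 0.273. Supplying EDF= closes 1.979 − 1.961 = 0.018 of it, and 0.018/0.273 is about 7%.

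**The case against.** The strongest objection is that the effect is too small to matter. A simulation of the ANCOVA contrast (6000 runs, 50 per arm, a correctly specified normal imputation model) gave these rejection rates, default against small-sample df: 0.0558 against 0.0543 at 5% missing, 0.0515 against 0.0507 at 10%, and 0.0495 against 0.0475 at 20%. The Monte Carlo standard error is about 0.003. The two rules differ by only 0.001 to 0.002, and at 20% missing the default rule is not above nominal. The last column of the table is therefore a tail area that takes the Barnard–Rubin df as exact, not a demonstrated error rate. The study is also declared not powered for significance, and MI is only a sensitivity analysis. All of this stands, and it limits the point to a minor one. It does not make the coded reference distribution right.

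A reader might infer that the missing EDF= is why a borderline dose could look more significant under MI than in the primary analysis. The documents do not support that. SAP 4.7.2 and 5 openly leave the MI comparisons unadjusted, and that accounts for about 93% of the gap in critical value. The gap would largely remain after the fix.

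A reader might also infer that the primary result is affected, because a sentence in SAP 4.2.9.1 still assigns MCMC MI to the primary efficacy analyses. SAP 4.7.1 and the declared change in SAP 5 say otherwise.

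Finally, the listing is incomplete: SAP 7.1.4 outputs ttest1 but pools ttest2, and the step between is not shown. That step cannot supply the df, since EDF= is an option of the MIANALYZE statement. It does matter for the fix, because pooling by Class may mix arm means with the difference.

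**Conclusion.** The point holds and is minor. The coded MI intervals are about 0.9–1.0% too narrow for the ANCOVA and the combined-dose t-test, and 1.3–1.5% too narrow for the single-dose t-tests. Tail areas are about 0.052 and 0.053 in place of 0.050.

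These figures assume 150 analysed subjects in equal arms and 3–15% missing information. At 50% missing information the narrowing would be 1.7% (ANCOVA) and 2.55% (single-dose t-test). Smaller analysed sets would widen it slightly. The effect of rounding imputed grades was not modelled.

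The effect is confined to the MI sensitivity analyses and stands alone only for Overall OTX-DED against HV and the unadjusted t-tests. The observed-data primary analysis is untouched.

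**What to change.** Add EDF= to both MIANALYZE calls, computed from the analysed counts in each population (mITT and PP) and not from the planned size:

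- ANCOVA contrasts and LS means: N − 4.
- Each t-test difference: n1 + n2 − 2 (about 98 for one dose against HV and 148 for combined doses against HV at planned size).
- Any single-arm mean pooled in the same t-test step: n − 1 (about 49 for one planned arm). Pool these in a separate call, because one EDF= value cannot serve both the arm means and the difference.

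Show the step that creates ttest2, state the rule in SAP 4.2.9.1, and bring that section's remaining reference to MI as primary into line with SAP 4.7.1 and 5. The cost is a few lines of code and one sentence of text. No new data or design change is needed.

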7.1.4. SAS codes to run t-test on MI data

```

/* SAS code below for testing group 1 vs group 3*/
ods output statistics=ttest1;
proc ttest data=din;
  where TRTPN in (1 3) ;
  by AVISIT PARAMN INPUT;
  class TRTPN;
  var CHG;
run;

ods output parameterestimates=pdif;
proc mianalyze data=ttest2;
  modeleffects mean;
  stderr stderr;
  by AVISIT PARAMN Class;
run;

```

7.1.5. SAS codes to run ANCOVA (using PROC MIXED) on Observed data and LOCF

Sponsor:	Ocular Therapeutix, Inc.		
Protocol:	OTX-DED-2020-201		
Document Version No.:	V1.0	Document Date:	11NOV2021

```
*** PROC MIXED ***;
ods output LSMESTIMATES=ls1(rename=(label=PARAMETER)) DIFFS=dun1;
proc mixed data=din;
by PARAMN AVISITN;
CLASS TRTPN (ref=last);
MODEL CHG=TRTPN BASE;
lsmeans TRTPN / cl pdiff=control('3') adjust=Dunnett;
LSMESTIMATE TRTPN "OTX-DED 0.2MG" 1 0 0,
"OTX-DED 0.3MG" 0 1 0,
"Overall OTX-DED" &WG1. &WG2. 0,
"HV" 0 0 1,
"OTX-DED 0.2MG vs HV" 1 0 -1,
"OTX-DED 0.3MG vs HV" 0 1 -1,
"Overall OTX-DED vs HV" &WG1. &WG2. -1 / cl;
run;
```

7.1.6. **SAS codes to output 95% CI for proportions using Clopper-Pearson method and 95% CI for the proportion difference using Chan and Zhang (1999) method using observed and LOCF data**

```
ods output RiskDiffCol1=freq1(where=(ROW in ("Row 1" "Row 2" "Difference")));
FishersExact=freq2(where=(NAME1="XP2_FISH"));
proc freq data=din;
where TRTPN in (1 3) and avisitn=4;
table TRTPN*AVALN / norow nocol nopercent fisher;
exact riskdiff(method=score);
run;
```
